7.3.3.4 Adverse Events Featuring a Severe Symptom

Any AE meeting the criteria for severe as defined in [Section 7.6](#) will be reported as an AEI.

7.3.3.5 Adverse Events Associated with Use of Epinephrine

Adverse events may result in epinephrine use. Upon awareness of such an event, site staff will report it within 24 hours using the AEI form, independent of severity or relatedness, or whether it was administered in the CRC or at home. If the epinephrine was used as part of an allergic reaction that meets criteria for anaphylaxis, an accidental food allergen exposure, an AE featuring a severe symptom, or an SAE, the use need not be reported separately. The intent of this AEI is to capture events that may be occurring that do not fall into one of these other categories.

7.3.4 Unexpected Adverse Event

An AE is “unexpected” when its nature (specificity) or severity is not consistent with applicable product information, such as safety information provided in the package insert, the investigational plan, the Investigator’s Brochure, or the protocol.

7.3.5 Clinically Significant Laboratory Results

An abnormal test result usually warrants reporting as an AE in the following situations:

- The test result is associated with clinically significant symptoms or signs and/or;
- The test result requires additional diagnostic testing or medical/surgical intervention and/or;
- The test result leads to a change in dosing or discontinuation of study treatment and/or;

- The test results are regarded as clinically significant by the investigator and/or medical monitor.

7.4 Adverse Event Monitoring and Recording

7.4.1 Monitoring Procedures

All AEs will be recorded from the time of signing of the informed consent form (ICF) through the Early Discontinuation/Exit Visit, including during dosing hiatus.

AE may be identified during subject visits or during the review of the subject diary. Each occurrence of an AE should be recorded separately (eg, daily abdominal pain).

All signs and symptoms associated with an AE should be recorded.

The investigator will treat subjects experiencing AEs appropriately and observe them at suitable intervals until their symptoms resolve or their status stabilizes.

Each AE will be followed from its onset until the event is resolved or medically stable or until Early Discontinuation/Exit Visit, whichever occurs first. AEs ongoing at the time that IP is discontinued may not be determined to be medically stable until 30 days after the End of Treatment Period, in which case additional monitoring after the Early Discontinuation/Exit Visit may be required.

Any new event or experience that was not present at Screening/Baseline or worsening of an event present at Screening/Baseline will be reported as an AE. Unchanged, chronic conditions are not AEs and should not be recorded on the AE form of the eCRF.

Each subject will be provided a diary log to record any AEs between study visits. Additionally, AEs may be discovered through any of the following methods:

- Observing the subject
- Questioning the subject, which should be done in an objective manner
- Receiving an unsolicited complaint from the subject
- Review of medical records/medical notes

Skin prick test reactions are not considered AE unless the reaction, or a complication from the procedure, is considered an SAE, as defined in [Section 7.3.1.1](#).

Food challenge reactions that occur in the clinic are captured on study specific forms and are not reported on an AE form (to avoid duplicate reporting) unless the event is considered an SAE, as defined below ([Section 7.3.1.1](#)).

- As study product is not used in the DBPCFCs, no AEs occurring from Screening DBPCFC can be treatment-related (referring to treatment with study product).
- For food challenge reactions that occur at the Exit DBPCFC, it will also usually be the case that study product was not the cause of the reaction, as study product is not

used in the challenge. There is, however the possibility that dosing with study product in the days prior to Exit DBPCFC could contribute to a reaction encountered during the challenge. The investigator must determine if dosing with study product in the days prior to Exit DBPCFC likely contributed to any observed reaction. If so, the investigator should indicate the level of the relatedness, and provide a brief explanation as to the manner in which prior dosing with study product was thought to be contributory.

7.4.2 Recording Procedures

All AEs will be recorded from the time of signing of the ICF through the Early Discontinuation/Exit Visit. Recording of these AEs into the eCRF is described below in the eCRF completion guidelines. In addition, SAE and AEI will be entered in a respective AE form as detailed in the AE form completion guidelines. Completion of appropriate eCRF and AE form is summarized in [Table 7](#) below.

Any event that meets the definition of an SAE ([Section 7.3.1.1](#)) will also be reported to the drug safety vendor using an SAE report form as described in [Section 7.9.1](#) in addition to completing the AE form. SAE follow-up reports should include, as applicable, hospital admittance notes, hospital discharge summary, clinical notes, resolution date, treatment, and any other pertinent information regarding the event. Reporting should not be delayed in order to provide these documents. In the event of a death, other supporting data (eg, death certificate, medical notes) should be included. Medical notes, with subject identifiers redacted, can be scanned and attached to the AE form as well.

Table 7: Adverse Event Recording

Adverse Event Type	eCRF	PV Form	Severity	Timeline	F/U
Serious Adverse Event	AE	SAE Form		< 24 hours	Y
AEI: Anaphylaxis	Allergy AE	AEI Form*	Muraro/EAACI	< 24 hours	Y
AEI: Allergic Reactions	AE	AEI Form*	CoFAR	< 24 hours	Y
AEI: Gastrointestinal AE resulting in dosing disruption	AE	AEI Form*	NCI-CTAE	< 24 hours	Y
AEI: Accidental Food Allergen Exposure	Allergy AE	AEI Form*		< 24 hours	Y
AEI: AE associated with epinephrine use	Con Meds	AEI Form*		< 24 hours	Y
AEI: Severe AE	AE	AEI Form*		< 24 hours	Y
Other: Food Challenge	FC	SAE only		< 24 hours	Y
Other: Pregnancy	Appropriate visit lab form	Pregnancy Form	NCI-CTAE	< 24 hours	Y
Other: Non-serious	AE	AEI only		< 7 days	Y

* Unless the AEI fulfills the seriousness criteria, in which case an SAE form should be completed.

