3.3 Exit DBPCFC

All subjects who reach the targeted daily dose of 300 mg and maintain that dose through the Maintenance Period will undergo an Exit DBPCFC. The Exit DBPCFC will be performed in accordance with PRACTALL guidelines, but starting at a dose of 3 mg of peanut protein (except for subjects who reacted to 1 mg in their Screening DBPCFC; these subjects will be required to start their Exit challenge at 1 mg; [Section 6.6.2](#)) and requiring progression in a fixed sequence ([Table 3](#)), without repeating any dose. Also, the Exit DBPCFC will include a 600 mg challenge dose, and the top challenge dose will be capped at 1000 mg.

The same vehicle food should be used for the Exit DBPCFC as was used for the Screening DBPCFC.

For each subject, a Blinded Evaluating Physician (Blinded Assessor) is to be designated to assess the tolerability of the challenge doses presented in the DBPCFC. The Blinded Evaluating Physician, who is assessing and managing subject symptoms on the food challenge days, is not to be involved directly in the oversight of study product dosing or the assessment or management of AEs during the initial escalation, up-dosing, or maintenance phases of the study; nor should he or she be involved in the food challenge material preparation on the food challenge days. To the extent practicable, the same Blinded Evaluating Physician who determines DLS in the Screening DBPCFC should determine DLS in the Exit DBPCFC.

Each subject will be unblinded after he/she completes the DBPCFC, all major data queries to date (ie, queries that could influence allocation to 1 or another analysis population) for the subject have been resolved, and the follow-on study ARC008 is available at the study site. Subjects may continue blinded study treatment and have clinic visits every 4 weeks in ARC010 until ARC008 is available, unless specified otherwise ([Section 3.4](#)). To maintain the study blind overall, individual unblinding information should only be distributed to designated team members on a need-to-know basis as instructed by Aimmune.

Subjects who do not reach the target dose of 300 mg/d by Week 40 are not eligible for the Exit DBPCFC. These subjects will be unblinded once the database has been locked and unblinded.

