6.11 Visit Intervals and Windows

Screening

The Screening Period assessments should be completed within 28 days (Day -27 to Day 0).

Initial Escalation

The Initial Escalation Day 1 visit occurs within 10 days of the second day of the Screening DBPCFC and must occur within 6 weeks of signing of the consent/assent form (preferably by 28 days). The exceptions to this are if a subject experiences an AE as a result of the DBPCFC, or due to scheduling difficulties, in which case an extension to the Screening window should be agreed with the medical monitor.

Up-dosing Period

For all Up-dosing Visits, which occur every 2 weeks, there is a \pm 3-day visit window. Regardless of visit intervals subjects must continue with daily dosing of IP.

Maintenance Period

The Maintenance Period lasts for approximately 12 weeks but may be extended up to a maximum of 16 weeks or to a maximum of study duration of 56 weeks, whichever is shorter ([Section 6.3.3.3](#)). There is a \pm 3-day visit window for all visits in the Maintenance Period.

The first Maintenance Visit is 2 weeks after the 300 mg Up-dosing Visit. The next 3 visits are at 6, 10, and 12 weeks after the 300 mg Up-dosing Visit. If at 12 weeks after the 300 mg Up-dosing Visit the subject has maintained a dose of 300 mg/d for approximately 12 weeks, without the use of symptomatic therapy for at least the last 4 weeks, the Exit Visit will be performed. If that is not the case, then the subject will continue in the study for up to 4 more weeks of 300 mg dosing before proceeding to the Exit Visit.

Exit Visit

The Exit Visit will occur after 12 to 16 weeks after a subject commenced dosing at 300 mg/d.

Early Discontinuation Visit

An Early Discontinuation Visit should occur 14 to 16 days from the last dose of IP.

Unscheduled Visits

Unscheduled Visits may occur at any time during the study.

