7.8.2 SAE Recording and Reporting Procedures

All SAEs will be reported to the sponsor from the time of signing of the ICF through the Early Discontinuation/Exit Visit (at least 14 days after the last AR101 dose). If the investigator becomes aware of a SAE in a subject treated by him or her with a suspected causal relationship to the IP that occurs after the end of the study, the investigator shall without undue delay, report it to the sponsor.

SAEs will be recorded on the AE CRF. All centers are obligated to report SAEs within 24 hours of their occurrence and/or the site's knowledge of the event to the sponsor. The following attributes will be assigned:

- Description
- Date of onset and resolution (if known when reported)
- Severity
- Assessment of relatedness to test article
- Action taken

The site investigator will apply his or her clinical judgment to determine whether an AE is of sufficient severity to require that the subject be removed from treatment. If necessary, an investigator will suspend any trial procedures and institute the necessary medical therapy to protect a subject from any immediate danger.

Subsequent review by regulatory health authority(ies), the DSMC, institutional review board (IRB)/ EC, or the sponsor(s) may suspend further trial treatment or procedures at a site. The study sponsor(s) and the regulatory health authorities retain the authority to suspend additional enrollment and treatments for the entire study as applicable.

1. Notify the site's investigator.
2. Complete and transmit an AE form through the EDC system. Information regarding an SAE report must be recorded in the subject's medical chart.
3. Complete and submit an SAE Form in accordance with the SAE completion guidelines.

4. SAE follow-up reports should include, as applicable, hospital admittance notes, hospital discharge summary, clinical notes, resolution date, treatment, and any other pertinent information regarding the event. Reporting should not be delayed in order to provide these documents.
5. In the event of a death, the SAE form must be completed and transmitted along with other supporting data (death certificate, medical notes, etc).

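### AE recording (7.4.1, 7.4.2) and routine SAE reporting (7.8.2) end at the Early Discontinuation/Exit Visit, but Appendix 1 footnote w collects AEs to 30 days after treatment, and blinded dosing may continue after Exit

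*Protocol*

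**What the plan says.** **Recording of AEs.** Section 7.4.2 says "All AEs will be recorded from the time of signing of the ICF through the Early Discontinuation/Exit Visit". Section 7.4.1 runs recording "through the Early Discontinuation/Exit Visit, including during dosing hiatus". It follows each event "until the event is resolved or medically stable or until Early Discontinuation/Exit Visit, whichever occurs first", then allows extra monitoring because "AEs ongoing at the time that IP is discontinued may not be determined to be medically stable until 30 days after" the end of treatment.

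**Reporting of SAEs.** Section 7.8.2 has sites report SAEs "through the Early Discontinuation/Exit Visit (at least 14 days after the last AR101 dose"). A later sentence in 7.8.2 adds SAEs "with a suspected causal relationship to the IP that occurs after the end of the study". Section 3.5 defines the end of the study as the last visit of the last subject.

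**Visits and dosing.** Section 6.4 places the Early Discontinuation Visit 14 to 16 days after the last dose. For the Exit Visit, section 6.11 says "The Exit Visit will occur after 12 to 16 weeks after a subject commenced dosing at 300 mg/d". Section 3.3 then says "Subjects may continue blinded study treatment and have clinic visits every 4 weeks in ARC010 until ARC008 is available, unless specified otherwise". Sections 3.4 and 6.5 and Appendix 1 footnote bb repeat this permission and withhold it from subjects who did not tolerate 300 mg at the Exit challenge.

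**Other windows.** Appendix 1 footnote w collects AEs and allergic symptoms from consent until 30 days after the subject completes study treatment. Sections 3.6 and 7.1 say safety events are captured throughout the study.

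**The concern.** The recording sections close the window at a visit, whereas footnote w closes it at a fixed time after the last dose. For anyone who finishes the trial the two differ. For a child who keeps taking daily blinded IP after the Exit challenge, the visit comes before the last dose, so on a plain reading of 7.4.2 routine AE recording stops while the child is still on allergen.

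The likely result is that sites behave differently: one working from 7.4.2 stops, and one working from footnote w carries on. Safety is a secondary objective, and the subjects are aged 4 to 17. The suspension rule in 7.11.1 counts hospital admissions caused by dosing, so it relies on SAE reporting that does not lapse while dosing continues. A later analysis plan cannot recover events that sites were told they need not record.

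**Working it through.** The protocol gives no figure to reproduce here. The check compares the stated windows and counts days.

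**Step 1. End points as stated**

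| Place | What it governs | End point |
|---|---|---|
| 7.4.1, 7.4.2 | recording of AEs | Early Discontinuation/Exit Visit |
| 7.8.2, first rule | reporting of SAEs | same visit, with a 14-day parenthesis |
| 7.8.2, later rule | suspected related SAEs only | begins after the end of the study |
| Appendix 1, footnote w | collection of AEs | 30 days after treatment is completed |
| 7.8 | how long each event is evaluated | at most 30 days after treatment |
| 3.6, 7.1 | capture of safety events | throughout the study |

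The explicit 30-day collection rule is in footnote w alone. Section 7.8 limits how long an event is evaluated; it does not say when new events stop being recorded.

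**Step 2. Gap between the visit cut-off and footnote w**

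Gap = (last dose + 30 days) − cut-off visit.

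- Early discontinuer, visit 14 to 16 days after the last dose: 30 − 16 = 14 days to 30 − 14 = 16 days.
- Completer who stops IP at Exit, visit at about the last dose: 30 − 0 = about 30 days.
- Completer who continues blinded IP for W days after Exit: W + 30 days, of which W are on drug.

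W is not in the protocol. It is zero where ARC008 is already open, and 3.3, 3.4, 6.5 and footnote bb set no maximum. As an illustration only, one, two or three of the 4-weekly intervals give 28 + 30 = 58, 56 + 30 = 86 or 84 + 30 = 114 days.

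**Step 3. The 14-day parenthesis in 7.8.2**

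It matches the Early Discontinuation Visit (14 to 16 days after the last dose). It does not match an Exit Visit held at the end of maintenance, because 6.5 requires 300 mg/d for the 4 weeks immediately before the Exit challenge. If it is read as keeping SAE reporting open until 14 days after the last dose, the end point is still 30 − 14 = 16 days short of footnote w.

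**Step 4. SAEs between a subject's Exit Visit and the end of the study**

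The first rule in 7.8.2 ends at the subject's visit. The later rule starts only at the study-level end. An SAE in between, even one suspected to be caused by IP, falls clearly under neither.

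**Step 5. Events that do not depend on the cut-off**

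Section 7.1 requires anaphylaxis to be reported within 24 hours for any event after consent. Section 7.3.3.5 does the same for AEs treated with epinephrine, subject to its exceptions for events reported under another category. Neither has an end date. The conflict therefore matters most for other AEs and for SAEs outside those categories.

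**The case against.** **The Exit Visit may stay open.** Appendix 1 puts unblinding in the Exit Visit column, footnote bb makes it wait for ARC008, and 6.5 has questionnaires completed after unblinding. On that reading the wait lies inside the visit and 7.4.2 covers it. This is arguable, so it would be too strong to say that the 14-day parenthesis is false of every Exit Visit. But 6.11 fixes the visit at 12 to 16 weeks after the first 300 mg/d dose, and the 30-day conflict remains on either reading.

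**The 7.8.2 parenthesis may extend SAE reporting.** It can be read that way for a child still on IP. The named end point is still the visit, and 14 days is not 30.

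**Other text already covers the period.** Sections 3.6 and 7.1 do, and the schedule has AE monitoring at Maintenance and Unscheduled Visits. The CRF and AE-form completion guidelines, which are not at hand, may settle practice. This makes loss of events less likely, but it leaves two incompatible instructions in the protocol. Appendix 1 has no column for the continuation visits.

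**The effect may be small.** It is nil for on-drug time where ARC008 is open, and the events of greatest concern have their own rules. That stands, and it limits the severity.

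**Conclusion.** The contradiction is real and in current operative text. It affects 14 to 16 days after the cut-off visit for early discontinuers, about 30 days for completers who stop at Exit, and the continuation period plus 30 days for those who stay on blinded IP. It should be corrected, but it does not touch any efficacy result.

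A reader might infer more than the documents support on three points:

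- *That on-drug events will certainly be lost.* Sections 3.6, 7.1 and footnote w point the other way, so the supported statement is that capture may differ between sites.
- *That the exposure at stake can be bounded.* Section 1.4 mentions a 56-week limit on blinded placebo therapy. From that one could derive a wait of at most 56 − (20 + 12) = 24 weeks. That sentence is rationale, and the sections permitting continuation do not repeat it. Carrying over ARC001 tolerance rates to count subjects would also be unsafe, because 9.4 notes that ARC001 enrolled subjects reacting at a lower cumulative dose. With no waiting time and no event rate at 300 mg/d, the number of events lost cannot be computed.
- *That suspected related SAEs stay reportable under 7.8.2 during the wait.* The clause that suggests this applies only after the last visit of the last subject.

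The on-drug part of the conclusion assumes that some sites reach Exit Visits before ARC008 opens and that the visit is timed as 6.11 says. The 30-day conflict needs neither assumption.

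**What to change.** 1. In the recording sentences of 7.4.1 and 7.4.2, and in 7.8.2, replace the visit cut-off with: until 30 days after the last dose of IP in ARC010, including any blinded dosing after the Exit DBPCFC. Delete the 14-day parenthesis in 7.8.2.
2. Do not put a 30-day limit with a whichever-is-first clause into the follow-up wording of 7.4.1, 7.8 or footnote w. It would clash with 3.2 and 4.3.2, which follow ongoing AEs until they resolve or stabilise, and with the later part of footnote w itself. Align the follow-up wording with 3.2 and 4.3.2, and leave the gastrointestinal follow-up in 7.3.3.2 unchanged.
3. State in footnote bb that AEs are monitored at the 4-weekly continuation visits.
4. Add one line saying whether ARC010 or ARC008 records events in subjects who roll over within the 30 days.

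The cost is a wording amendment, and the continuation visits already take place. The downside is slightly longer AE collection and one more period in the safety listings.

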7.5 Data Safety Monitoring Committee

Although the safety of peanut OIT overall is well established, a DSMC will monitor the study for safety. The DSMC will meet at time points defined in the DSMC charter to review accruing safety data. The committee will consist of individuals with extensive multicentre clinical study experience drawn from the fields of clinical immunology (specifically food allergies) and biostatistics. These individuals will be entirely independent of the conduct of the study. Further details will be provided in the DSMC Charter.

7.6 Severity Grading

The investigator is to assign severity grades to AEs. Depending on the type of AE, different severity grading systems will be used in this study.

- The severity of allergic reactions will be graded according to the definitions developed by the CoFAR group ([Appendix 4](#)).
- The severity of anaphylactic reactions will be graded according to the EAACI system for grading the severity of anaphylactic reactions ([Appendix 3](#)).
- The severity of all other AEs will be graded according to the National Cancer Institute's Common Terminology Criteria for Adverse Events (NCI-CTCAE) system. The purpose of using the NCI-CTCAE system is to provide standard language to describe AEs ("toxicities") and to facilitate tabulation and analysis of the data and for assessment of the clinical significance of treatment-related toxicities. The NCI-CTCAE provides a term and a grade that closely describes the AE. Each participating site will receive copies of the grading scales and event descriptions. For additional information and a printable version of the NCI-CTCAE v. 4.03 manual, consult the NCI-CTCAE website, <http://ctep.cancer.gov/reporting/ctc.html>.

For AEs not included in the NCI-CTCAE listing, they are also to be graded on a scale from 1 to 5, according to the General Grade Definition provided below:

Grade 1	Mild	Transient or mild discomforts (< 48 hours), no or minimal medical intervention/therapy required, hospitalization not necessary (non-prescription or single-use prescription therapy may be employed to relieve symptoms (eg, aspirin for simple headache, acetaminophen for post-surgical pain).
Grade 2	Moderate	Mild to moderate limitation in activity, some assistance may be needed; no or minimal intervention/therapy required, hospitalization possible.
Grade 3	Severe	Marked limitation in activity, some assistance usually required; medical intervention/therapy required, hospitalization possible.
Grade 4	Life-threatening	Extreme limitation in activity, significant assistance required; significant medical/therapy intervention required, hospitalization or hospice care probable.
Grade 5	Death	Death

For additional information and a printable version of the NCI-CTCAE v. 4.03 manual, consult the NCI-CTCAE website, <http://ctep.cancer.gov/reporting/ctc.html>.

